## **6.6 PHARMACOKINETIC AND PHARMACODYNAMIC ANALYSES**

Not Applicable

## **7 SAFETY ANALYSIS**

Safety assessments will include clinical chemistry, hematology, coagulation (prothrombin time or International Normalized Ratio (INR)), PRA, vital signs, adverse events, symptom directed physical exams and Duplex ultrasound assessments. Summaries of all safety assessments will be reported by visits where data are collected.

### **7.1 EXTENT OF EXPOSURE**

There are two exposures that will be summarized:

1. Subject exposure during the study period is defined as the length of time from implant to death or early termination (e.g. lost to follow up, withdrew consent etc.).
2. Subject exposure to a patent conduit used for hemodialysis is defined as the length of time from first cannulation to explant, abandonment, death, transplant or early termination (e.g. lost to follow up, withdrew consent etc.).

Subject exposure during the study period and exposure to a patent study conduit used for hemodialysis will be reported by study arm at each analysis time point. Descriptive statistics will be provided for days of exposure. Overall exposure will be summarized in total subject-years. This will be calculated as follows:

Exposure in subject-years = Sum of duration of exposure in days (for all subjects in treatment group) / 365.25.

Frequency and percentages of subjects falling into the following different exposure ranges will also be summarized:

- >0 to =< 6 months (182 days),
- 6 months to =< 12 months (365 days),
- 12 months to =< 18 months (547 days),
- 18 months to =< 24 months (730 days),
- >24 months to =< 60 months (1825 days), and
- 60 months.

A listing of exposure data will be provided.

## 7.2 ADVERSE EVENTS

See the study protocol for the definition of adverse events (AE). The investigator's verbatim term for all adverse events will be mapped to System Organ Class (SOC) and preferred terms using the current version of the Medical Dictionary for Regulatory Activities (MedDRA).

From a technical regulatory perspective the HAV is a biologic medicinal product while the ePTFE graft is a device. For the purposes of this study and to allow for better cross-treatment arm comparisons of safety, and given that the IMP is a biologic drug, all events will be reported as if both arms were drugs.

AEs will be summarized as treatment-emergent AEs (TEAEs) for the Safety analysis set.

An AE will be considered a TEAE if the onset of the event is on or after the start of the anesthesia for the implant surgery. If an AE start date is completely missing, then the AE will be considered as TEAE unless it can be determined that the AE end date occurred prior to the anesthesia for the implant surgery. If the AE start date is partially missing then the start date will be imputed as described in Section 4.4.

### 7.2.1 Adverse Event Severity

See the study protocol for definition of adverse event severity grading levels.

### **Adverse Event Relationship to IMP**

See the study protocol for definition of adverse event relationship to IMP. The relationship of an AE to IMP and study procedure will also be assessed by the sponsor. The sponsor assessment categories for relationship are unrelated/unlikely related or at least possibly related.

### **Serious Adverse Event**

See the study protocol for definition of serious adverse event.

### **Adverse Events Summaries**

An overall summary of all TEAEs will be presented overall and by treatment group and will include the following:

- the number and percentage of subjects experiencing a TEAE
- the number and percentage of subjects experiencing a TEAE by strongest relationship to IMP assessed by Principal Investigator and sponsor
- the number and percentage of subjects experiencing a TEAE by strongest relationship to study procedure(s) assessed by Principal Investigator and sponsor
- the number and percentage of subjects experiencing a TEAE by greatest intensity (see Section 9.3 of study protocol for details on intensity)
- the number and percentage of subjects experiencing a TEAE leading to IMP abandonment
- the number and percentage of subjects experiencing a treatment emergent SAE (TESAE)
- Deaths

In the overall summary of TEAEs table, besides tabulating the number and percentage of subjects, the total number of TEAE episodes will also be provided. If a subject has repeated episodes of a particular TEAE, all episodes will be counted in the summary table.

In addition to an overall summary, the following safety data with no inferential statistics will be provided:

- All Treatment Emergent AEs by SOC and PT
- All Serious AEs by SOC and PT
- All Treatment Emergent AEs leading to outcome of death by SOC and PT
- All Treatment Emergent AEs by SOC, PT and greatest severity
- All Treatment Emergent AEs by SOC, PT and greatest causal relationship to IMP and study procedure assessed by Principal Investigator and sponsor

- All Treatment Emergent AEs leading to study discontinuation by SOC and PT

For these summaries, if a subject has repeated events of a particular TEAE, only the most severe event or the event with the strongest causal relationship to IMP will be counted in the summary tables.

### **Access-Related Infections**

In addition to the summaries indicated above in Section 7.2.4, the following access-related infection outputs are planned:

- Rate of access-related infections per 100 person-years of HAV/ePTFE graft use (i.e. censored at abandonment)
- Rate of access-related infections per 100 person-years over the 2-year post-implantation follow-up period

The analysis of access-related infections will be based on adjudicated events using a standardized definition of access-related infections. The infection rates will be compared using a Poisson regression model with treatment group and the surgical placement stratification variable as factors, if no overdispersion is present. Otherwise, a negative binomial regression will be used to adjust for overdispersion. The analysis will be conducted using a two-sided test at the alpha=0.05 level of significance. The following aspects associated with access-related infections will be described and summarized:

- The timing of first study access-related infection relative to the initiation of dialysis using the implanted conduit
- The use of intravenous antibiotics
- The need for hospitalization
- Other potential factors identified by the CEC

### **Events of Special Interest other than Access-Related Infections**

Adverse events constituting or leading to events of special interest related to interventions and infections according to Section 2.2.2.5 will be presented descriptively. The analyses will include:

- Aneurysms: incidence rate of clinically significant (requiring intervention) and non-clinically significant (no interventions) aneurysms (100 person-years of retaining secondary patency since implantation) will be reported.

- Pseudo-aneurysms: incidence rate of clinically significant (requiring intervention) and non-clinically significant (no interventions) pseudo-aneurysms (100 person-years of HAV/ePTFE graft use since first cannulation) will be reported.
- Steal syndrome, thrombosis, stenosis, and bleeding of study access: Number and percent of subjects experiencing an event, events by severity, and events requiring interventions by severity will be tabulated by treatment group. Time to onset of first event will be presented descriptively.

All AEs and SAEs will be presented in individual listings. The listing will contain the following information: treatment group, verbatim term, SOC, PT, intensity, relationship to treatment, date and day of onset, date and day of resolution, treatment given to treat the adverse event, the outcome, whether the event was an SAE, whether it led to withdrawal and whether it is a TEAE. Listings will be sorted by subject identification number, non-imputed onset date, SOC, and PT. If the onset date is completely missing, then these events will be presented first. If the onset date is missing a month or a day, then these events will be presented before any complete dates.

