4.2.2 Secondary Endpoints

4.2.2.1 Key Secondary Endpoints:

Efficacy

Time to loss of Primary Patency from implantation

- Defined as 'the interval from the time of access placement until any intervention designed to maintain or reestablish patency, access thrombosis or the measurement of patency', i.e., patent without interventions ([Sidawy 2002](#)).

Safety

Access-related infections ([CDC 2013](#))

4.2.2.2 Other Secondary Endpoints:

Efficacy

1. Rate of interventions required to achieve/maintain Secondary Patency
2. Time to loss of Primary Assisted Patency from implantation
 - a. Defined as 'the interval from the time of access placement until access thrombosis or the time of measurement of patency, including intervening manipulations (surgical or endovascular interventions) designed to maintain the functionality of patent access' i.e., patent without an intervention to clear a thrombus ([Sidawy 2002](#)).
3. Histopathological remodeling of any study conduit (based on any samples collected).
4. The efficiency of dialysis as assessed by $spKt/V_{urea}$ (obtained from dialysis unit for a subset of subjects).

Safety

1. Frequency and severity of AEs
2. Study conduit dilatation:
 - a. True aneurysm formation (conduit lumen diameter > 9 mm)
 - b. Pseudo-aneurysm formation
3. Study conduit spontaneous rupture
4. Anastomotic bleeding or spontaneous rupture

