9.1 Definition of Adverse Events

An AE is defined as any untoward medical occurrence in a subject administered an IMP or has undergone study procedures and which does not necessarily have a causal relationship with this treatment. An AE can therefore be any unintended sign (including an abnormal laboratory finding), symptom, or disease temporally associated with the use of the IMP, whether or not related to the IMP.

It should be noted that from a technical regulatory perspective the HAV is a biologic medicinal product while the ePTFE graft is a device. For the purposes of this study and to allow for better cross-treatment arm comparisons of safety, and given that the IMP is a biologic drug, all events will be reported as if both arms were drugs.

An abnormality identified during a medical test (e.g., laboratory parameter, vital sign, ECG data, PE) should be defined as an AE only if the abnormality meets one of the following criteria:

- Induces clinical signs or symptoms
- Requires active intervention

- Requires interruption or discontinuation of the IMP
- The abnormality or test result is clinically significant in the opinion of the investigator.

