10.4 Safety Analysis

The safety analysis will be conducted in the safety population.

For each of the two treatment groups, the access-related infection rate will be computed in 2 ways:

- Rate of access-related infections per 100 person-years of HAV/ePTFE use (i.e., censored at abandonment)
- Rate of access-related infections per 100 person-years over the 2-year post-implantation follow-up period

These analyses will be based on adjudicated events using a standardized definition of access-related infections ([CDC 2013](#)).

For each of the 2 definitions, the infection rates in the two arms will be compared using a Poisson regression model with treatment group and the randomization stratification variable as factors. This analysis will be conducted using a two-sided test at the alpha=0.05 level of significance.

All other safety data will be described only (i.e., no inferential statistics).

For the analysis of study conduit dilatation and aneurysm formation, descriptive data will be presented by Visit. In addition, the number of study conduits showing true aneurysm formation (internal conduit diameter >9 mm) or pseudo-aneurysm will be reported.

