#### 2.2.0.4 ***Other Secondary Safety Endpoints***

- Frequency and severity of adverse events
- Study conduit dilatation:
  - True aneurysm formation (conduit lumen diameter > 9mm)
  - Pseudo-aneurysm formation
- Study conduit spontaneous rupture
- Anastomotic bleeding or spontaneous rupture

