#### 2.2.0.5 ***Events of Special Interest***

Events of special interest related to interventions and infections will be evaluated and include the following:

- Study conduit abandonment
- Thrombosis/ thrombectomy
- Angioplasty or stenting
- Access-related infection

- Pseudo-aneurysm or true aneurysm (conduit lumen diameter > 9mm) formation
- Study conduit spontaneous rupture
  - Iatrogenic injuries are not an Event of Special Interest and should be reported as an AE
- Revision or ligation of the study conduit
- Study conduit removal
- Steal syndrome

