## **7.6 SUBJECT AND GRAFT STATUS**

Summaries of subject status (alive or deceased), study conduit patency/usability, evidence of clinically significant aneurysm formation of the study conduit by clinical examination, need for interventions to maintain or restore patency of the study conduit and reasons for study conduit abandonment will be reported by frequency counts and percentages. Listings of the subject and graft status including the parameters provided above will be provided.

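### The SAP takes its only aneurysm rate from adverse events and omits the protocol's count of conduits above 9 mm, so symptom-free dilatation on duplex can be missed in that rate

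*SAP*

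**What the plan says.** **Definition.** Protocol 4.2.2.2 and SAP 2.2 (Other Secondary Safety Endpoints) define true aneurysm by lumen diameter alone, with no symptom or intervention required. The SAP list of Events of Special Interest uses the same threshold: "Pseudo-aneurysm or true aneurysm (conduit lumen diameter > 9mm) formation". Comparing true aneurysm and pseudo-aneurysm rates between arms is a stated safety objective.

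**Analysis promised in the protocol.** Under Protocol 10.4, dilatation data are to be described by visit and "the number of study conduits showing true aneurysm formation (internal conduit diameter >9 mm) or pseudo-aneurysm will be reported".

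**Analysis specified in the SAP.** The SAP 7.2 section on Events of Special Interest other than access-related infections opens: "Adverse events constituting or leading to events of special interest related to interventions and infections according to Section 2.2.2.5 will be presented descriptively". Under it comes the "incidence rate of clinically significant (requiring intervention) and non-clinically significant (no interventions) aneurysms", per 100 person-years with secondary patency retained since implantation. SAP 7.6 separately tabulates "evidence of clinically significant aneurysm formation of the study conduit by clinical examination". SAP 7 and 8 plan duplex summaries by visit and a listing, without classifying conduits at 9 mm.

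**When a test result is an adverse event.** Protocol 9.1 says that an abnormality found on a medical test "should be defined as an AE only if the abnormality meets one of the following criteria": it produces signs or symptoms, needs active intervention, leads to interruption or discontinuation of the product, or is clinically significant in the investigator's view.

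**The concern.** The endpoint is a measurement, but the stated source of the rate is a reporting category with its own entry conditions. A lumen above 9 mm that is silent, untreated and not thought significant meets the endpoint definition and none of the conditions in Protocol 9.1. Read as written, the SAP 7.2 rate has no place for it, although the no-intervention category shows that the authors meant to count untreated aneurysms.

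The protocol gives reasons to want this number right. Section 2.1 notes a high risk of aneurysmal dilatation with earlier biological conduits. Section 2.5.1 reports one aneurysmal dilatation of the HAV in Phase 2 and relies on regular ultrasound to recognise such cases. The trial is open-label, and aneurysm is not among the events that the Clinical Events Committee adjudicates. Whether a silent reading enters the rate would therefore rest on an unblinded investigator's opinion.

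**Working it through.** The documents state no aneurysm rate, so there is no figure of the plan to reproduce. The check compares the provisions and then expresses the possible loss as a proportion.

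**Step 1. Follow one case through the provisions.** Take a scheduled duplex showing a lumen above 9 mm, with no symptoms, no intervention, and no judgement of clinical significance.

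| Provision | Is the case counted? |
|---|---|
| Endpoint definition (Protocol 4.2.2.2, SAP 2.2) | Yes, by diameter |
| Event of Special Interest (Protocol 4.2.3, SAP 2.2) | Yes, by diameter |
| Count in Protocol 10.4 | Yes, by diameter |
| Adverse event under Protocol 9.1 | Not required |
| SAP 7.2 rate | Only if it is also an adverse event, as worded |
| SAP 7.6 status table | No; limited to clinically significant cases on clinical examination |
| SAP 7 and 8 duplex summaries and listing | Visible, but not counted as a case |

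The definition and the SAP 7.2 rate therefore disagree for this case. The protocol count that would settle the matter has no counterpart in the SAP.

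**Step 2. Follow-up after Month 24.** Protocol 9.4 then limits reporting to HAV-related serious adverse events and all Events of Special Interest. Duplex continues at Months 36, 48 and 60 (Protocol 8.6.2.1), and the SAP 7.2 person-time has no stated 24-month limit. In that period, the Event of Special Interest record is the natural source for a non-serious aneurysm, and an adverse-event numerator fits poorly.

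**Step 3. Size of the loss.** Let s be the share of conduits above 9 mm that are entered as adverse events, counting one event per conduit. Person-time is defined by patency and does not depend on adverse-event status, so

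reported rate = s × measured rate.

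For illustration, assume that 5% of the planned 175 HAV conduits exceed 9 mm: 175 × 0.05 = 8.75, about 9. Neither the 5% nor any value of s comes from the documents.

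| s | Conduits counted (8.75 × s) | Proportion (5% × s) |
|---|---|---|
| 1 | 8.75 | 5% |
| 0.75 | 6.56 | 3.75% |
| 0.5 | 4.38 | 2.5% |
| 0.25 | 2.19 | 1.25% |

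**Step 4. Effect on the comparison.** The reported rate ratio is the measured ratio × (s in HAV ÷ s in ePTFE). If s is equal in both arms, the ratio is unchanged and the absolute difference shrinks by the factor s. If s differs, both are distorted. For example, 0.5 against 0.75 multiplies the ratio by 0.5 ÷ 0.75 = 0.67.

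**The case against.** The sponsor can answer that capture does not rest on Protocol 9.1. A true aneurysm above 9 mm is itself an Event of Special Interest. Protocol 8.3.9 requires assessment for these events at every postoperative visit, with prompt eCRF entry, and Protocol 9.4 has all of them reported through five years. The SAP 7.2 sentence points to the list that carries the 9 mm threshold and expressly includes aneurysms without intervention. On that view the gap is one of wording. Protocol 10.4 still stands, and nothing in the SAP cancels it. The endpoint is a descriptive secondary safety measure.

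Much of this stands and limits the point. It shows that the data should exist and that the authors meant to count untreated cases. It does not show that the SAP uses that record: its stated source is adverse events, and Events of Special Interest are a separate reporting category. That Protocol 10.4 survives is a reason for the SAP to specify its count.

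Three stronger readings are tempting, and the documents do not support them:

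- **The endpoint is counted from clinical examination.** SAP 7.6 is a separate status table; the incidence rate is in SAP 7.2.
- **Silent dilatation vanishes from safety reporting.** Duplex results are summarised by visit and listed, and SAP 4 gives the maximum for continuous variables, so a recorded diameter above 9 mm would be visible. What is missing is the number of conduits.
- **The no-intervention category is emptied.** An aneurysm that causes symptoms or is judged significant, but is not treated, is still an adverse event and falls there. The category is thinned.

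**Conclusion.** The point holds in a limited form. The SAP does not implement the Protocol 10.4 count, and its only aneurysm rate is drawn from adverse events. A measured endpoint can therefore be under-counted there, to an extent set by open-label judgement.

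The size is unknown. The understatement is 1 − s: none if every such case is entered as an adverse event, 25% at s = 0.75, 75% at s = 0.25. These values are assumptions, and the relation presumes one event per conduit with every case arising from a recorded diameter.

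A reader might infer that the under-count always favours the conduit that dilates more. That is true of the absolute difference when s is equal in both arms, but the ratio is then unaffected. When s is unequal, the direction depends on which arm is under-recorded.

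No primary or key secondary result is touched. The change is worth making because it is cheap and concerns a known risk of biological conduits.

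**What to change.** In SAP 7.2, count a true aneurysm for every conduit that has either of the following, whether or not it was entered as an adverse event, dated at the first such record:

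- any recorded duplex lumen diameter above 9 mm; or
- any reported Event of Special Interest of true aneurysm.

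Both sources are needed. The duplex procedure visualises the full length of the conduit, but the only diameter it names is mid-conduit. Dilatation elsewhere may be found only in the Event of Special Interest record. The rule should stay within recorded data and not presume a full-length maximum that the documents do not show being collected.

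Report the Protocol 10.4 count and the incidence rate by arm on the existing person-time. Keep the intervention / no-intervention split as a breakdown of that total. Reconcile duplex, Event of Special Interest and adverse-event records before each database lock. SAP 7.6 can stay if it is labelled as a status table and not the endpoint count.

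The cost is SAP wording, one derivation and one reconciliation. Data collection and patient care do not change. The reported aneurysm count may be higher.

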3.2 Secondary Objectives

3.2.1 Key Secondary Objectives:

Efficacy

To compare the Primary Patency of the HAV with that of the ePTFE graft.

Safety

To compare the rate of access-related infections for the HAV with that of the ePTFE graft.

3.2.2 Other Secondary Objectives:

Efficacy

1. To compare the rate of interventions needed to maintain/restore patency of the HAV with that of the ePTFE graft.
2. To compare the Primary Assisted Patency of the HAV with that of the ePTFE graft.
3. To describe the histopathological remodeling of samples from HAV and ePTFE grafts.
4. To compare the efficiency of dialysis with the HAV with that of the ePTFE graft in a subset of subjects.

Safety

1. To compare the safety and tolerability of the HAV with that of the ePTFE.
2. To compare the relative rates of true aneurysm and pseudo-aneurysm formation.

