4.3 Duration of Study Participation

Each subject will be followed at study specific visits until he/she has completed 24 months of follow-up after implantation (irrespective of patency status). After 24 months, subjects with a patent study conduit will be followed (while the study conduit remains patent) for up to 5 years (60 months) post-implantation at routine study visits.

The expected duration of the clinical investigation is 76 months (initiation of enrollment through completion of data collection).

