  - Rate of interventions defined as the number of interventions per subject per year while the conduit is patent (i.e. has not been abandoned). Results will be provided for Day 0 to Month 18 and overall (Day 0 to total follow-up period). Intervention rate for each 6-month interval will be reported.
  - The rate of interventions (number of interventions per 100 person-years) in the two arms will be compared using a Poisson regression model with treatment group and the surgical placement stratification variable as factors, if no overdispersion is present. Otherwise, a negative binomial regression will be used to adjust for overdispersion.
  - The number and rate of thrombectomies, angioplasties and revisions will be analyzed separately
- Interventions that failed to maintain/restore Secondary Patency. In the case when a delayed decision is made to abandon the study conduit (e.g. delayed and then failed thrombectomy), the date of abandonment is back dated to the initial recognition of the thrombosis. Any interventions performed after this date of abandonment will then be considered to have failed to maintain/restore Secondary Patency. Summaries for these interventions will include:
  - Proportion of subjects who had at least one failed intervention
  - Number of failed interventions per subject
  - Distribution of how many had 1, 2, 3 ... failed interventions

- Superiority analysis of the time to loss of Primary Assisted Patency using log-rank test at the 0.05 significance level and similar censoring rules discussed for the primary endpoint.
- Histology assessments of any conduits will be summarized descriptively. Summaries will include the following:
  - The proportion of subjects in whom a sample has been collected
  - The histological findings in each arm will be described and listed
- Dialysis efficiency as assessed by spKt/Vurea (obtained from dialysis unit for a subset of subjects) will be summarized descriptively. The most recent available data prior to the study visits will be used for the analysis.

All secondary endpoints will be summarized by treatment group using counts and percentages for the categorical variables, and n, mean, median, standard deviations, minimum and maximum for the continuous endpoints.

All secondary analyses will occur after all subjects complete at least 18 months post implantation.

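### SAP 7.2 gives crude percentages for steal, thrombosis, stenosis and bleeding at the study access, so the arm figures depend partly on how long the conduits last

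*SAP*

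**What the plan says.** SAP 7.2, under Events of Special Interest other than Access-Related Infections, groups steal syndrome, thrombosis, stenosis and bleeding at the study access in one bullet. The planned summary is "Number and percent of subjects experiencing an event, events by severity, and events requiring interventions by severity will be tabulated by treatment group". The only time element is "Time to onset of first event will be presented descriptively". The bullet gives no person-time denominator and no rule for abandonment.

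The neighbouring outcomes are handled differently:

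- Aneurysms, same section: incidence rate over "100 person-years of retaining secondary patency since implantation) will be reported".
- Pseudo-aneurysms, same section: incidence rate over "100 person-years of HAV/ePTFE graft use since first cannulation) will be reported".
- Infections, SAP 7.2 Access-Related Infections: "Rate of access-related infections per 100 person-years of HAV/ePTFE graft use (i.e. censored at abandonment".
- Interventions, SAP 6.2: "Rate of interventions defined as the number of interventions per subject per year while the conduit is patent (i.e. has not been abandoned". Rates are also given for each 6-month interval.

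Protocol 4.3 keeps every subject in the study for "24 months of follow-up after implantation (irrespective of patency status". After Month 24 only subjects whose conduit is still patent are followed, up to Month 60. Protocol 9.4 still requires Events of Special Interest to be reported in that period, and the list in Protocol 4.2.3 includes steal syndrome and thrombosis.

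A secondary objective in Protocol 3.2.2 is "To compare the safety and tolerability of the HAV with that of the ePTFE". Protocol 10.4 limits safety data other than infections to description, without inferential statistics.

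**The concern.** The four events belong to the study access. Once the conduit is abandoned, the subject is essentially no longer at risk of them but still counts in the denominator. If the arms lose conduits at different speeds, they have different time at risk within the same nominal follow-up. That is the difference the primary endpoint measures, so the crude percentages are not independent of patency.

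For an event that arises steadily while the conduit is in place and does not end it, the arm with shorter conduit life has less opportunity to show events. Equal hazards would then appear as unequal percentages, and a real difference could be masked. What is at stake is a misleading side-by-side safety table. No test depends on it.

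**Working it through.** **Inputs from the documents.** SAP 11 assumes 12-month secondary patency of 60% for ePTFE, and of 66% (non-inferiority) or 76% (superiority) for HAV, with 350 subjects allocated 1:1. SAP 6.1 cites annual mortality of about 20%.

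**Assumptions.** Conduit loss is exponential. The event hazard h while the conduit is in place is the same in both arms, at 0.05 to 0.5 per year. The documents give no rates for these events, so a range is used.

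**The plan's own figure.** Superiority at 76% versus 60% is stated to have 90% power. The hazard ratio is ln(0.76)/ln(0.60) = 0.537. With 175 per arm and a fixed 12 months, expected events are 175 × (0.40 + 0.24) = 112. Schoenfeld power is Φ(√112/2 × |ln 0.537| − 1.96) = 90.8%, which agrees. Counting the extra follow-up from 16 months of accrual gives about 162 events and 97.7%. The choice does not affect what follows, which uses only the patency rates.

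**Time at risk.** The loss hazard is L = −ln(12-month patency): 0.511 per year for ePTFE, 0.416 for HAV at 66%, 0.274 for HAV at 76%. Conduit-years per subject over T = 2 years are (1 − e^(−LT))/L:

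- ePTFE: (1 − 0.36)/0.511 = 1.25
- HAV at 66%: 1.36
- HAV at 76%: (1 − 0.578)/0.274 = 1.54

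**Crude percentage for events that do not end the conduit.** P = h/(h + L + d) × (1 − e^(−(h + L + d)T)), where d is the death hazard. With d = 0 and h = 0.05:

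- ePTFE: 0.05/0.561 × (1 − e^(−1.122)) = 6.0%
- HAV at 76%: 0.05/0.324 × (1 − e^(−0.649)) = 7.4%

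| h per year | ePTFE (60%) | HAV (66%) | HAV (76%) | ePTFE/HAV ratio (66%) | ePTFE/HAV ratio (76%) |
|---|---|---|---|---|---|
| 0.05 | 6.0% | 6.5% | 7.4% | 0.92 | 0.82 |
| 0.10 | 11.5% | 12.5% | 14.1% | 0.93 | 0.82 |
| 0.20 | 21.3% | 23.0% | 25.8% | 0.93 | 0.83 |
| 0.50 | 42.9% | 45.9% | 50.8% | 0.94 | 0.84 |

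The true hazards are equal in every row. At 76% patency, an ePTFE hazard 24% to 32% higher would appear as equal percentages. With d = −ln(0.8) = 0.223 the ratio at 76% is 0.83 to 0.86. At 18 months without deaths it is 0.85 to 0.87. At 60 months, the same formula gives about 16% versus 23% (h = 0.1) and 49% versus 63% (h = 0.5).

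**Thrombosis.** If a share q of abandonments is itself a thrombosis, the leading factor becomes (h + qL)/(h + L). At 24 months, ePTFE versus HAV at 76%:

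| q | h = 0.20 | h = 0.50 |
|---|---|---|
| 0 | 21.3% vs 25.8% | 42.9% vs 50.8% |
| 0.25 | 35.0% vs 34.7% | 53.9% vs 57.8% |
| 0.50 | 48.6% vs 43.6% | 64.8% vs 64.8% |
| 1 | 75.9% vs 61.3% | 86.8% vs 78.8% |

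The direction reverses at about q = 0.25 for h = 0.20, and at about q = 0.50 for h = 0.50.

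**Early events.** Suppose the event can occur only in the first 30 days, with a 10% risk in both arms if no conduit were lost. The crude percentages are 9.8% and 9.9%, almost undistorted. One overall rate gives 9.8/1.25 = 7.8 versus 9.9/1.54 = 6.4 per 100 person-years, a spurious 18% advantage for the longer-lasting conduit. Over the first 6 months alone, conduit-years per subject are (1 − √0.60)/0.511 = 0.441 and (1 − √0.76)/0.274 = 0.467. The rates are then about 22.2 and 21.2, a gap of about 5%.

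**The case against.** The strongest reply is that a reader might infer that the faster-losing arm looks safer on all four events. The documents do not support that. Protocol 2.4.3.2 makes thrombosis the last step in every graft failure, and the censoring rules date a delayed abandonment back to the recognised thrombosis. Thrombosis is thus a cause of conduit loss as well as an event cut short by it, and its crude percentage can run the other way. This stands. So does the point on early events: Protocol 2.4.3.2 ties very early failures largely to surgical technique, and crude percentages serve such events well.

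A reader might also infer a biased test, or that a worse conduit could be hidden. Neither follows. The tabulation is descriptive, and conduit loss is itself the primary endpoint, with Kaplan-Meier patency reported by arm.

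The hazards are assumed. At 0.05 to 0.10 per year and 66% patency, the gap is only 0.5 to 1.0 percentage points.

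The claim that exposure is already handled elsewhere stands only in part. SAP 6.2 gives rates for thrombectomies and angioplasties, which bear on thrombosis and stenosis. These are procedures rather than events, and they are listed under interventions that succeeded. Failed interventions get proportions and counts only. SAP 6.2 gives no event rate for steal or bleeding. The patent-conduit exposure in SAP 7.1 starts at first cannulation, which under Protocol 8.4.8 should not precede day 28, so it omits early time at risk. A descriptive onset time does not supply a denominator.

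**Conclusion.** The point holds in a limited form. The four summaries have no time-at-risk adjustment, unlike the neighbouring outcomes, and are therefore confounded with patency. For steal, bleeding and stenosis that does not end the conduit, arising throughout conduit life, the crude percentage understates the faster-losing arm by about 16% to 18% relative to the other at 24 months under the superiority planning rates, and by about 6% to 8% under the non-inferiority rates. These sizes rest on exponential loss, equal constant hazards within the assumed range, and no deaths. Including deaths at the cited rate changes them little.

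For thrombosis the confounding remains, but its direction cannot be stated in advance. Events confined to the first month are hardly affected. The gap is clearest for steal and bleeding, for which no exposure-adjusted figure is planned. It also extends to the long-term report, because after Month 24 only subjects with a patent conduit are still observed. The primary analysis is untouched.

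**What to change.** In SAP 7.2, keep the crude counts for all four events. Beside them add, by arm with 95% CI, events per 100 person-years of retained secondary patency since implantation, shown by 6-month interval as SAP 6.2 already does for interventions. State that a thrombosis that leads to abandonment counts as an event.

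Cumulative incidence of first event, with death and abandonment (when not itself the event) as competing events, is another useful display, above all for events that cluster early. It should accompany the rates rather than replace them: with complete follow-up it reaches the same value at 24 months as the crude percentage, so it shows timing but does not remove the dependence on patency.

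The aneurysm rates already require this person-time, so no new data are needed. The cost is SAP wording and a few table columns. The one real drawback is that a single overall person-year rate can mislead for early-clustered events, as the 7.8 versus 6.4 example shows. The interval display is therefore part of the change.
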